6.2. Exclusion Criteria

Patients will be excluded from study enrollment if they meet any of the following criteria at screening:

Medical Conditions

- [15] Have any other condition (including known drug or alcohol abuse, or psychiatric disorder including eating disorder) that precludes the patient from following and completing the protocol
- [16] Have hypoglycemia unawareness as judged by the investigator
- [17] Have had more than 1 episode of severe hypoglycemia (defined as requiring assistance due to neurologically disabling hypoglycemia) within the last 6 months prior to screening

- [18] Have had more than 1 emergency room visit or hospitalization due to poor glucose control (hyperglycemia or diabetic ketoacidosis) within 6 months prior to screening (Visit 1)
- [19] Have cardiovascular disease within the last 6 months prior to screening, defined as stroke, decompensated heart failure New York Heart Association class III or IV (see [Appendix 6](#)), myocardial infarction, unstable angina pectoris, or coronary arterial bypass graft
- [20] Renal:
- History of renal transplantation
 - Currently receiving renal dialysis
 - Serum creatinine >2.0 mg/dL (177 $\mu\text{mol/L}$) at screening
- [21] Hepatic: Have obvious clinical signs or symptoms of liver disease (for example, acute or chronic hepatitis, or cirrhosis) or elevated liver enzyme measurements as indicated below at screening (Visit 1):
- Total bilirubin level (TBL) $\geq 2X$ the upper limit of normal (ULN) (with the exception of Gilberts Disease) as defined by the central laboratory,
OR
 - Alanine aminotransferase (ALT) $\geq 3X$ ULN as defined by the central laboratory
OR
 - Aspartate aminotransferase (AST) $\geq 3X$ ULN as defined by the central laboratory
- [22] Malignancy: Have active or untreated malignancy, have been in remission from clinically significant malignancy (other than basal cell or squamous cell skin cancer) for less than 5 years, or are at an increased risk for developing cancer or a recurrence of cancer in the opinion of the investigator
- [23] Have any hypersensitivity or allergy to any of the insulins or excipients used in this trial
- [24] Have hypersensitivity or allergy to any of the ingredients in the standardized test meal (MMTT) (for example, nut allergy)
- [25] Hematologic: Have had a blood transfusion or severe blood loss within 90 days prior to screening or have known hemoglobinopathy, anemia, or any other traits known to interfere with measurement of HbA1c
- [26] Have presence of clinically significant gastrointestinal disease (for example, clinically active gastroparesis associated with wide glucose fluctuations) in the investigator's opinion

- [27] Have excessive insulin resistance defined as having received a total daily dose of insulin >1.5 U/kg at the time of screening

Prior/Concomitant Therapy

- [28] Glucocorticoid therapy: Receiving chronic (lasting longer than 14 consecutive days) systemic glucocorticoid therapy (including IV, intramuscular, SC, or oral, but excluding topical, intraocular, intranasal, intra-articular and inhaled preparations) or have received such therapy within 8 weeks immediately prior to screening (Visit 1) with the exception of replacement therapy for adrenal insufficiency
- [29] Have been on a treatment regimen that includes regular human insulin or any premixed insulins within 90 days prior to screening (Visit 1)
- [30] Have used insulin human inhalation powder (Afrezza®) within 90 days prior to screening (Visit 1)
- [31] Have used CSII within the 90 days prior to screening (Visit 1)
- [32] Receiving any oral or injectable medication intended for the treatment of diabetes mellitus other than insulins in the 90 days prior to screening (Visit 1)

Prior/Concurrent Clinical Trial Experience

- [33] Are currently enrolled in any other clinical trial involving an IP or any other type of medical research judged not to be scientifically or medically compatible with this study
- [34] Have participated, within the last 30 days in a clinical trial involving an IP. If the previous IP has a long half-life, 3 months or 5 half-lives (whichever is longer) should have passed
- [35] Have previously completed or withdrawn from this study or any other study investigating LY900014 after receiving at least 1 dose of the IP

Other Exclusions

- [36] Are investigator site personnel directly affiliated with this study and/or their immediate families. Immediate family is defined as a spouse, parent, child, or sibling, whether biological or legally adopted
- [37] Are Lilly employees (including employees, temporary contract workers, or designees responsible for the conduct of the study)
- [38] Are unable and/or unwilling to provide informed consent, to make themselves available for the duration of the study, to comply with the use of a data collection device to directly record data, or to abide by study procedures

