- [9] Have access to a telephone or alternative means for close monitoring and communications, and have access to a reliable cellular signal for transmission of the electronic clinical outcomes assessment (eCOA) data

- [10] Have refrigeration in the home or have ready access to refrigeration for storage of insulin therapy
- [11] Patient whom the investigator has determined can be randomized and maintain the treatment regimens based on their previous medical history including insulin dosing regimens, hypoglycemic episodes, and glycemic control
- [12] Capable of, willing, and desirous to do the following:
 - a) Inject insulin with the use of an insulin injection device (insulin pen) according to included directions
 - b) Perform self-BG monitoring including 10-point SMBG on designated days (patients using a personal continuous glucose monitoring [CGM] or flash glucose monitoring [FGM] device for insulin dosing decisions must still use the study glucose meter according to the protocol)
 - c) Keep records in eCOA as required by this protocol
 - d) Participate in two 4-hour mixed-meal tolerance tests (MMTTs) and consume a standardized meal for the tests
 - e) Follow an algorithm for basal insulin adjustment and individualized prandial insulin dosing using fixed pattern adjustment or carbohydrate counting as agreed upon with the investigator
 - f) Comply with the use of the study insulin and scheduled visits
- [13] Considered healthy (apart from T1D) upon completion of medical history, physical examination, vital signs, electrocardiogram (ECG), and analysis of laboratory safety variables, as judged by the investigator

Informed Consent

- [14] Have given written informed consent to participate in this study in accordance with local regulations.

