7.7. Concomitant Therapy

Guidance on restrictions for concomitant therapies is provided in [Table ITRM.8](#).

Table ITRM.8. Concomitant Medications

Drug Class	Acute Use	Chronic Use	Safety Follow-Up and Insulin Lispro Antibody Follow-Up Periods	Conditions
NPH, insulin glargine U-300, insulin detemir, insulin degludec U-200	No	No	Yes	
Regular human insulin	No	No	No	
Afrezza® (inhaled insulin), or premixed human or premixed analog insulin	No	No	No	
Any noninsulin diabetes treatment therapy	No	No	No	
Systemic glucocorticosteroid (including IV, intramuscular, SC, or oral but excluding topical, inhaled, intraocular, intra-articular, or intranasal preparations)	Yes	No	No	During the lead-in period, allow 1-time use for ≤7 consecutive days. During all other study periods, allow 1-time use for ≤14 consecutive days.

Abbreviations: IV = intravenous; NPH = neutral protamine Hagedorn; SC = subcutaneous.

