8.1. Discontinuation from Study Treatment

In the event that a patient is discontinued from the study treatment, the investigator should encourage the patient to remain in the study for continued safety monitoring.

Lilly recognizes the importance of complete data collection. This study includes elements to minimize missing data. Randomized patients who are discontinued from IP before study completion are encouraged to remain in the study for continued monitoring. For patients who remain in the study after early discontinuation of IP, both efficacy (including HbA1c) and safety data will be collected at scheduled visits. The difference between stopping IP and discontinuing the study will be explained to patients as part of the informed consent, and patients will be encouraged to continue in the study even if they stop study drug. In addition, study site investigators will be trained on the importance of complete data collection, with additional re-education of sites and patients as necessary.

8.1.1. *Permanent Discontinuation from Study Treatment*

Patients will be discontinued from the IP in the following circumstances:

- The investigator may decide that the patient should stop IP. If this decision is made because of an AE, SAE, or a clinically significant laboratory value, the study drug is discontinued for that patient and appropriate measures are to be taken. Lilly or its designee is to be alerted.
- The patient may decide to stop IP.
- If the patient becomes pregnant.
- If an investigator, study site personnel performing assessments, or patient is unblinded, the patient must discontinue IP.
- If the patient, for any reason, requires treatment with another therapeutic regimen or therapeutic agent that has been demonstrated to be effective for treatment of the study indication. Discontinuation from IP should occur prior to introduction of the new agent.
- Use of prohibited concomitant medication, see [Table ITRM.8](#).
- Patient has not taken IP for more than 14 consecutive days.

Discontinuation of the IP for abnormal liver tests **should be considered** by the investigator when a patient meets one of the following conditions after consultation with the Lilly designated medical monitor:

- ALT or AST >8X ULN.
- ALT or AST >5X ULN for more than 2 weeks.
- ALT or AST >3X ULN and total bilirubin level(TBL) >2X ULN or prothrombin time >1.5X ULN.

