Eligibility	Inclusion/ Exclusion	Hematological conditions	Mixed (monitoring and clinical database)	CRF Pre-existing Conditions panel data using MedDRA terms that are considered as relevant hematological conditions by the CRP/CRS to indicate not compliant with entry criteria #25 Also identified by CRA as captured in sCTMS.
Eligibility	Inclusion/ Exclusion	Previous noninsulin antihyperglycemic medications	Mixed (monitoring and clinical database)	CRF Prior Diabetes Therapies / Concomitant Therapy panel data to indicate not compliant with entry criteria #32. Also identified by CRA as captured in sCTMS.
Eligibility	Inclusion/ Exclusion	Previous insulin therapy	Mixed (monitoring and clinical database)	CRF Prior Diabetes Therapies / Concomitant Therapy panel data to indicate not compliant with entry criteria #3, #4, #29, #30, #31. Also identified by CRA as captured in sCTMS.
Investigational Product	Treatment Assignment/ Randomization Error		Mixed (monitoring and clinical database)	IWRS data entry errors that impact patient stratification, for example, lab data indicated different strata from IWRS stratification report. Dispensing error: Patient was assigned to a treatment, but site gave a different treatment to the patient.
Investigational Product	Unblinding		Non Programmable (monitoring)	Any inadvertent unblinding affecting, patients, investigator, or sponsor.
Investigational Product	Patient Took Medication Not Fit for Use		Non Programmable (monitoring)	Study Drug not fit for use administered to patient.
Investigational Product	Other	Use of expired CT material	Non Programmable (monitoring)	Also identified by CRA as captured in sCTMS.

Description of Important Protocol Deviations

Category	Sub-categories	Description	Source	Methods of Identification
Study Procedures	Violation of Discontinuation Criteria		Mixed (monitoring and clinical database)	Patients not discontinued from treatment and/or study despite having met protocol specified discontinuation criteria. Also identified by CRA as captured in sCTMS Protocol Section 8.
Study Procedures	Excluded Conmeds		Mixed (monitoring and clinical database)	CRF Prior Diabetes Therapies / Concomitant Therapy panel data to indicate not compliant with entry criteria #28 and study-specific restriction on concomitant therapies Table ITRM.8 in the study protocol. Also identified by CRA as captured in sCTMS.

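### Criterion 28 admits patients on glucocorticoid replacement for adrenal insufficiency, but Table ITRM.8 bars that treatment in every study period and Section 8.1.1 then requires IP to be stopped

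*Protocol*

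**What the plan says.** Criterion 28 (Protocol 6.2) excludes systemic glucocorticoid therapy lasting more than 14 days in a row, whether current or within the 8 weeks before screening, "with the exception of replacement therapy for adrenal insufficiency".

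Table ITRM.8 (Protocol 7.7) governs the same class during the study: "Systemic glucocorticosteroid (including IV, intramuscular, SC, or oral but excluding topical, inhaled, intraocular, intra-articular, or intranasal preparations". Acute use is Yes, chronic use is No, and use in the safety and antibody follow-up periods is No. The conditions column allows a single course of up to 7 days in lead-in. For the rest it states: "During all other study periods, allow 1-time use for ≤14 consecutive days".

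Protocol 8.1.1 opens its list with "Patients will be discontinued from the IP in the following circumstances". One item is "Use of prohibited concomitant medication", with a pointer to Table ITRM.8.

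SAP 6.9, Table 6.3, treats two related things as important deviations. The Violation of Discontinuation Criteria row covers "Patients not discontinued from treatment and/or study despite having met protocol specified discontinuation criteria". The Excluded Conmeds row refers to both criterion 28 and Table ITRM.8. Adrenal insufficiency is mentioned nowhere else in either document.

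**The concern.** The entry rule and the on-study rule give opposite answers for the same patient on the same drug. The table row repeats the route exemptions of criterion 28 (topical, inhaled, intranasal and so on) but not its one exemption by indication. That looks like an omission rather than a decision to reverse the entry rule.

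What is at stake is how such a patient is handled. A site following the text admits someone the plan chose to admit, and must then take that person off study insulin for a treatment known at screening. A site that finds this unreasonable keeps the patient on IP and collects an important protocol deviation. Two sites can treat identical patients differently and each point to the protocol.

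**Working it through.** No figure in the plan needs reproducing. The check sets the rules side by side and counts days, assuming that replacement therapy is taken without interruption.

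1. **Entry.** Criterion 28: replacement for adrenal insufficiency does not exclude. The patient can enter lead-in if the other criteria are met.

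2. **Lead-in.** Table ITRM.8 allows 7 consecutive days, so the limit is passed on day 7 + 1 = 8. Lead-in lasts 8 × 7 = 56 days. Day 8 comes 7 days after Visit 2, which is 56 − 7 = 49 days, or 7 weeks, before the scheduled randomisation visit.

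3. **After randomisation.** The table allows 14 consecutive days, so the limit is passed on day 14 + 1 = 15. This is the latest date: the chronic-use column is a plain No with no grace period, and the patient is already a chronic user at Visit 8.

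4. **Consequence.** Section 8.1.1 makes stopping IP mandatory. Whether it bites in lead-in depends on what IP means. Section 7.2 counts lead-in insulin lispro among the IP assigned by the IWRS, and the Schedule of Activities has IP dispensed at Visits 2 and 5. Other places, such as the pregnancy-test footnote to that schedule and SAP Table 6.2, use IP for the randomised product. The conflict can therefore arise before randomisation, and on either usage it arises after it.

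5. **What follows for the analysis sets.**
   - *Stopped before randomisation:* if the patient is then not randomised, nothing is lost from the efficacy estimand, Completer or PP sets, since all are built from randomised patients. The loss is one patient the plan meant to include.
   - *Stopped after randomisation:* under SAP 6.1, HbA1c counts as on IP up to 14 days after the last dose; later values leave the efficacy estimand. The Week 26 visit is day 26 × 7 = 182, so its HbA1c is lost if the last dose is before day 182 − 14 = 168 (161 to 175 with the ±7-day window). The ITT estimand keeps whatever is collected. A stop before Week 26 also removes the patient from the Completer and PP sets, apart from the tolerance of under 3 days before Visit 18 in SAP 6.6.
   - *Kept on IP:* the patient fits Violation of Discontinuation Criteria and Excluded Conmeds. Neither is among the three deviations that SAP 6.9 lists as excluding from PP (no informed consent, a haematological condition interfering with HbA1c, missing HbA1c at baseline or primary endpoint).

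**The case against.** Several defences deserve an answer.

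- *The table is only guidance.* Section 7.7 does introduce it that way, but 8.1.1 attaches a mandatory consequence to it. The softer wording in 8.1.1, that stopping should be considered, applies only to abnormal liver tests.
- *Other criteria would keep these patients out.* Criterion 13 requires a patient "Considered healthy (apart from T1D) upon completion of medical history" and other checks, criterion 15 excludes any condition "that precludes the patient from following and completing the protocol", and criterion 11 asks for the investigator's judgement that the regimen can be maintained. These narrow who reaches the conflict. They do not put the exception into the table, and using them to refuse every such patient would leave the exception in criterion 28 with no effect.
- *The exception qualifies only the 8-week look-back.* Then current users would still be excluded, and for an ongoing treatment the exception would do almost nothing.
- *The sponsor can approve case by case.* Section 8.1.3 covers patients who did not meet the enrolment criteria. These patients do meet criterion 28.
- *A sensible site would never stop IP for this.* Probably so, and a site that carries the patient through lead-in has already read the table as not reaching replacement therapy. That lowers the practical risk, but it leaves the site departing from 8.1.1 as written.

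A reader might also infer that the two rules cannot both be obeyed. They can: a site may enrol the patient and then stop IP. The defect is that the later rule defeats the earlier exception.

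What stands from this side is the weight. The mismatch is real, but its reach is narrow.

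**Conclusion.** The inconsistency is clear on the text and nothing elsewhere in the documents resolves it. It is minor. The conclusion rests on three assumptions: replacement is continuous, 8.1.1 is applied as written, and the exception in criterion 28 covers current users. The part before randomisation also rests on the Section 7.2 usage of IP.

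Two stronger readings are tempting and should not be drawn.

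- *That the affected patient loses three of the four HbA1c visits in the efficacy estimand.* A last dose on day 14 or 15 gives an on-IP cutoff of day 28 or 29, which excludes Visits 13, 15 and 18 (days 56, 84 and 182) and can retain Visit 11 (day 28). But that is one assumed stopping date. An earlier stop can lose Visit 11 too, Visit 11 may itself fall anywhere from day 21 to 35, a later stop loses less, and a site applying the table literally could have acted in lead-in. It describes one hypothetical patient, not the trial.
- *That the primary comparison is at risk.* The documents give no prevalence of adrenal insufficiency in the enrolled population, so no number of patients can be stated, and no effect on the noninferiority conclusion is shown for either estimand.

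**What to change.** At the next amendment, add "with the exception of replacement therapy for adrenal insufficiency" to the systemic glucocorticosteroid row of Table ITRM.8, worded so that it covers lead-in, treatment and both follow-up periods. The 8.1.1 trigger and the two SAP Table 6.3 checks refer back to the protocol rules, so they follow without separate edits.

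If the sponsor does not want these patients, delete the exception from criterion 28 instead. That turns away whoever the exception would have covered.

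Either choice is one phrase. It needs ethics review and site notification, which is why it should be bundled rather than issued alone. It requires no extra patients, procedures or SAP revision.

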6.3. Lifestyle Restrictions

- Patients should be instructed not to donate blood or blood products during the study.

- Patients should be instructed to avoid major changes in dietary intake or physical activity during the 3 days prior to MMTT.

6.4. Screen Failures

Individuals who do not meet the criteria for participation in this study (screen failure) may not be rescreened. Retests are also not allowed, except for cases when results are not available from the original sample.

7. Treatments

7.1. Treatments Administered

This study involves a comparison of LY900014 and insulin lispro administered subcutaneously 0 to 2 minutes prior to the start of the meal for 52 weeks. In a third open-label treatment group, LY900014 will be administered postprandially (20 minutes after the start of a meal [LY900014+20]) for 26 weeks. [Table ITRM.2](#) shows the treatment regimens.

Table ITRM.2. Treatment Regimens

Regimen	Dose Strength	Dose Administration	Route of Administration	Timing of Administration
LY900014	100 U/mL	Individualized dosing	Subcutaneous	0 to 2 minutes before start of the meal
Insulin lispro	100 U/mL	Individualized dosing	Subcutaneous	0 to 2 minutes before start of the meal
LY900014+20	100 U/mL	Individualized dosing	Subcutaneous	20 minutes after the start of the meal

The investigator or his/her designee is responsible for the following:

- explaining the correct use of the IP to the patient including the importance of injection site rotation for both basal and prandial insulin
- explaining requirements for recording insulin doses and injection times to the patient
- verifying that instructions are followed properly
- maintaining accurate records of IP dispensing and collection
- at the end of the study, returning all used and unused IP to Lilly, or its designee, unless the sponsor and sites have agreed all unused medication is to be destroyed by the site, as allowed by local law

7.1.1. Packaging and Labeling

Clinical trial materials will be labeled as IP as appropriate, and according to the country's regulatory requirements. Study insulins (LY900014 and insulin lispro) will be supplied by Lilly or its representative, in accordance with current good manufacturing practices, and will be supplied with clinical trial lot numbers. Instruction for Use for the prefilled devices will be provided.

The blinded prefilled pens will contain a concentration of 100 U/mL in 3-mL cartridges of either LY900014 or insulin lispro. The open-label prefilled pens will contain a concentration of 100 U/mL of LY900014.

During the lead-in period, 100 U/mL insulin lispro will be provided using open-label prefilled pens.

7.1.2. Medical Devices

The medical devices provided for use in the study are prefilled pens. LY900014 prefilled pens are new investigational combination products.

7.2. Method of Treatment Assignment

Patients who meet all criteria for enrollment will be randomized to double-blind or open-label treatment at Visit 8. Assignment to treatment groups will be determined by a computer-generated random sequence using an interactive web-response system (IWRS). Patients will be randomized to double-blind LY900014, double-blind insulin lispro, or open-label LY900014+20 in a 4:4:3 ratio. Stratification will be by country, HbA1c stratum ($\leq 7.5\%$, $>7.5\%$ at Visit 7), type of basal insulin during the lead-in period (glargine U-100 or degludec U-100), and prandial insulin dosing plan at randomization (carbohydrate counting, pattern adjustment).

The IWRS will be used to assign all IP during the study, including insulin lispro during the lead-in period. The IWRS will be used to assign prefilled pens containing double-blind IP to each patient randomized to the 2 blinded treatment groups and prefilled pens containing open-label IP to each patient randomized to the LY900014+20 treatment group. Site personnel will confirm that they have located the correct prefilled pens by entering a confirmation number found on the prefilled pens into the IWRS.

